9.2 Sample Size Determination

9.2.1 PRIMARY EFFICACY ENDPOINT: SAMPLE SIZE AND POWER

Based on NLR

The trial sample size was evaluated and selected to assure adequate statistical power that the upper limit of the 95% CI for NLR will be smaller than 0.52. For design purposes we evaluate power and sample size using the variance from Table 9 equation E under the hypothesis that NLR = 0.20 with sensitivity = 0.90, specificity = 0.50, and 20% prevalence of large varices (i.e., 80 subjects with large varices = 0.2x400). A sample size of 400 participants (80 with large varices, 320 without) was selected to provide adequate power based on the following power characteristics:

		Power	for variou	ıs sample	sizes
NLR	FNR	380	400	420	440
0.20	0.048	0.78	0.80	0.82	0.84
0.19	0.045	0.82	0.84	0.86	0.87
0.18	0.043	0.86	0.88	0.89	0.91
0.17	0.041	0.89	0.91	0.92	0.93
0.16	0.038	0.92	0.93	0.94	0.95
0.15	0.036	0.95	0.96	0.96	0.97

Table 10: Initial Power Analysis for Selection of N-400

In this analysis 400 subjects provide over 80% probability/power of rejecting the rule-out hypothesis of NLR > 0.52 when the true NLR is smaller than 0.20. From Table 9 equation D, NLR = 0.2 corresponds to FNR = 0.048; thus, the trial has more than 80% power for FNR smaller than 5%. With 400 subjects, the upper limit of the 95% confidence will exclude NLR > 0.52 if the NLR in the trial is smaller than 0.27; that is, the threshold (critical value) for rejecting the NLR null hypothesis is NLR≤0.27 (corresponding to FNR smaller than 6.5%). This evaluation is based on the large-sample variance of equation E and is adequate for selecting the total sample size for the trial. A complete power evaluation of trial power with and without an interim analysis requires a simulation study as described in section 9.5.1.

Based on Predictive Value of a Negative Test (NPV)

NPV is the probability that a subject with DSI \leq 18.3 does not have varices, and the false negative rate is defined from NPV according to equation D in **Table 9**. The goal is to ensure that *NPV is suitably large and FNR* is suitably small. NLR can also be written in terms of NPV. From equation D, *NLR* <0.27 corresponds to FNR <6.5% and a NPV over 0.937. Similarly, the critical value rules out NLR > 0.52, which corresponds to NPV > 0.885 (FNR < 11.5%). The study sample size gives 80% power under the hypothesis that *NLR* = 0.2, which corresponds to FNR < 5%.

Impact of Dropout, Withdrawal, or Missing Data on Study Power: This is a very short-term study with maximum duration of a participant's participation of 100 days and a minimum participation of 3 days. We expect a low dropout rate – probably less than 5%. Nonetheless, we will recruit an excess of 5% of cases, N=420 total, to ensure enrollment of 400 evaluable cases.

Planned Interim Analysis: A single interim analysis is planned after the trial data set has compete DSI and EGD measurements on 250 participants. Details of the interim analysis can be found in Section 9.5.1.

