The HALT-C Training dataset (red marker with black border) showed that DSI 18.3 had sensitivity 0.95 and specificity 0.54 yielding a NLR of 0.0926, well within the shaded blue region. The upper limit of the 95% CI for NLR was 0.143, well below the upper limit of the 95% CI for the cv of 0.52. We anticipate that diagnostic performance of DSI 18.3 in the CLD Validation dataset will equal or exceed its performance in the HALT-C Training dataset, with sensitivity >95%. If that is the case, then specificity may drop below 0.50 as long as the observed NLR is <0.27. The mean value for specificity from the 10 published studies of LSM plus platelet count was 0.28 with a minimum of 0.13 and maximum of 0.44. Specificity \geq 0.28 will be considered acceptable, as long as the confidence interval rules out NLR > 0.52.

The following table shows specific values of sensitivity and specificity with 95% confidence intervals that are on the critical value line in **Figure 10**. The table shows the ranges of sensitivity and specificity that would be ruled out if the trial results are on the critical value line.

Spec	Specificity (95% CI)		ivity (95% CI)
0.25	(0.203, 0.297)	0.932	(0.878, 0.987)
0.30	(0.250, 0.350)	0.919	(0.859, 0.979)
0.35	(0.298, 0.402)	0.906	(0.841, 0.970)
0.40	(0.346, 0.454)	0.892	(0.824, 0.960)
0.45	(0.395, 0.505)	0.878	(0.807, 0.950)
0.50	(0.445, 0.555)	0.865	(0.790, 0.940)
0.55	(0.495, 0.605)	0.851	(0.774, 0.929)

Table 11: Values of sensitivity and specificity that are on the critical value line.

Evaluation of trial power: The initial power evaluation for selection of the total sample size (**Table 10**) uses the large sample variance approximation of **Table 9** equation E. A simulation study was designed and conducted to provide a full evaluation of trial power including the planned interim analysis. Power is a function of sensitivity, specificity as determined by NLR (specificity = (1-sensitivity)/NLR), and the prevalence of large varices. The simulation study calculated power as the proportion of 10000 simulated trials that satisfy the two performance goals (upper CI limit for NLR < 0.52 and sensitivity > 0.85). Key results of the simulation study are summarized in **Table 12**.

	Wi	thout Interim Analy	/sis	With Interim Analysis		sis
			20% prevalence o	f large varices		
NLR	Sensitivity = 0.85	Sensitivity = 0.90	Sensitivity = 0.95	Sensitivity = 0.85	Sensitivity = 0.90	Sensitivity = 0.9
0.52	0.020	0.017	0.011	0.020	0.015	0.007

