0.40	0.146	0.088	0.041	0.131	0.077	0.032
0.30	0.502	0.380	0.157	0.417	0.348	0.124
0.20	0.524	0.916	0.583	0.520	0.855	0.545
0.15	NA	0.930	0.910	NA	0.880	0.890
			25% prevalence o	f large varices		
0.52	0.021	0.021	0.012	0.019	0.017	0.010
0.40	0.170	0.107	0.054	0.151	0.100	0.041
0.30	0.515	0.462	0.193	0.450	0.422	0.172
0.20	0.515	0.944	0.696	0.523	0.888	0.668
0.15	NA	0.945	0.956	NA	0.902	0.951
	NA denotes combi	nations that produc	ce specificity = 1.0 a	and results that ca	nnot occur in a trial	

Table 12: Power for the SHUNT-V trial with and without interim analyses. The type I error rate is the power when NLR = 0.52 and is always smaller than the target one-sided 0.025 alpha level.

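### Section 9.2.1 states more than 80% power for FNR below 5%, but the 80% belongs to one sensitivity and specificity; at the same NLR and FNR with sensitivity 0.95, Table 12 gives 0.583 without and 0.545 with the interim

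*Combined protocol and SAP*

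**What the plan says.** Section 9.2.1 sets the design alternative first: power is evaluated with Table 9 equation E "under the hypothesis that NLR = 0.20 with sensitivity = 0.90, specificity = 0.50, and 20% prevalence of large varices". Table 10 then gives 0.80 at N=400 for NLR 0.20, rising to 0.96 at NLR 0.15. The text below the table reads "In this analysis 400 subjects provide over 80% probability/power of rejecting the rule-out hypothesis of NLR > 0.52" when the true NLR is below 0.20, and goes on: "NLR = 0.2 corresponds to FNR = 0.048; thus, the trial has more than 80% power for FNR smaller than 5"%. The NPV paragraph repeats the claim: "The study sample size gives 80% power under the hypothesis that" NLR is 0.2, which it equates with FNR below 5%. Section 1.1 gives the 80% with no alternative attached.

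Section 9.2.1 also says that a complete power evaluation needs simulation. Section 9.4.2 reports that simulation in Table 12 and states the governing fact: "Power is a function of sensitivity, specificity as determined by NLR" and prevalence. The same section expects sensitivity above 95% and adds: "If that is the case, then specificity may drop below 0.50 as long as the observed NLR is <0.27". Specificity of at least "0.28 will be considered acceptable, as long as the confidence interval rules out NLR > 0.52".

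**The concern.** The FNR sentence turns a result at one sensitivity and specificity into a property of FNR. Many pairs of sensitivity and specificity share an FNR of 4.8% at 20% prevalence, and they do not share a power. FNR is the quantity the plan uses to argue clinical acceptability (sections 2.3.1 and 2.3.4). A reader of 9.2.1 could therefore take it that any test with FNR under 5% has better than four chances in five of meeting the NLR goal. At one such point the plan's own simulation puts the chance nearer 55%.

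**Working it through.** **Inputs.** From 9.2.1: null NLR 0.52, N=400 (80 with large varices, 320 without), design point 0.90/0.50. From Table 9: equations D and E. From 9.5.1: 97.64% and 51.41% intervals at N=250 and 96.07% at N=400. The second goal is observed sensitivity of 0.85 or more.

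**1. Reproduce Table 10.** Power = Φ(ln(0.52/NLR)/√V − 1.96), with V from equation E.
- V = 0.90/(0.10×80) + 0.50/(0.50×320) = 0.1125 + 0.0031 = 0.1156; √V = 0.340.
- At NLR 0.20: 0.9555/0.340 − 1.96 = 0.85, so power is 0.802 (printed 0.80).
- Holding V at this value in every row reproduces all 24 cells. At N=400: 0.802, 0.842, 0.877, 0.908, 0.934, 0.955.

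Table 10 is correct, but no row represents another sensitivity.

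**2. FNR fixes only NLR.** Equation D at 20% prevalence: FNR = 1 − 1/(1 + NLR×0.25). NLR 0.20 gives 1 − 1/1.05 = 4.8%, whatever the sensitivity.

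**3. Same NLR and FNR, sensitivity 0.95.** Specificity = 0.05/0.20 = 0.25.
- V = 0.95/(0.05×80) + 0.75/(0.25×320) = 0.2375 + 0.0094 = 0.2469; √V = 0.497.
- 0.9555/0.497 − 1.96 = −0.04, so equation E power is 0.485.
- Table 12, by simulation, gives 0.583 without and 0.545 with the interim.

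**4. Simulated power for both goals.** Score test, at least 200,000 trials per point, N=400, 20% prevalence. Futility is triggered by either condition, except in the row marked *.

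| Sens | Spec | NLR | FNR | No interim | With interim |
|---|---|---|---|---|---|
| 0.92 | 0.40 | 0.200 | 4.8% | 0.860 | 0.831 |
| 0.93 | 0.35 | 0.200 | 4.8% | 0.790 | 0.759 |
| 0.944 | 0.28 | 0.200 | 4.8% | 0.658 | 0.617 |
| 0.95 | 0.25 | 0.200 | 4.8% | 0.587 | 0.543 |
| 0.95 | 0.28 | 0.179 | 4.3% | 0.736 | 0.698 |
| 0.95 | 0.30 | 0.167 | 4.0% | 0.817 | 0.784 |
| 0.95 | 0.31 | 0.161 | 3.9% | 0.851 | 0.823 |
| 0.96 | 0.28 | 0.143 | 3.4% | 0.855 | 0.825* |
| 0.95 | 0.54 | 0.093 | 2.3% | 1.000 | 0.996 |

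*Futility requires both conditions, as printed in 9.5.1. For the sensitivity 0.944 and 0.95 rows at specificity 0.25 to 0.31, the two futility readings differ by no more than about 0.001.

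At 0.95/0.25 the NLR goal alone has simulated power 0.586, so practically all the loss comes from the NLR interval.

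**5. The edge at 5%.** FNR of exactly 5% is NLR 0.2105. With the plan's own fixed variance, ln(0.52/0.2105)/0.340 − 1.96 = 0.70, so power is about 0.76. Between FNR 4.8% and 5% the sentence overstates equation E even on Table 10's own basis.

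**6. The with-interim figure at 0.90/0.50.** Table 12 prints 0.855. Simulation gives 0.852 if either futility condition stops the trial, but 0.915 if both are required, as 9.5.1 is worded. Interim futility probabilities are 0.123 and 0.012 respectively; Table 13 prints 0.118.

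**The case against.** The strongest reply is that the sentence has been lifted from its setting. The design point stands earlier in the same section, Table 10 is labelled an initial analysis, the paragraph is confined to that analysis, and it hands the full evaluation to a simulation that prints the lower figures. Much of this stands. It limits the harm, and it makes edits to the sentence about true NLR below 0.20 and to the NPV sentence largely redundant, since both are already tied to the stated hypothesis. It does not rescue the FNR sentence, whose inference the cited simulation contradicts.

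A second reply is that the affected region is narrow. This also stands. The 0.95/0.25 point lies below the 0.28 mark, although Table 11 lists specificity 0.25. The 0.28 statement is a rule for an observed result once the interval has excluded 0.52, not an alternative the plan claims to be powered for. Section 9.4.2 expects sensitivity above 95%, and at 0.96/0.28 power is already about 0.83 with the interim.

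A reader might also cite Table 12's 0.524 and 0.520 at sensitivity 0.85 as further counter-examples. They are not. Those values reflect the separate observed-sensitivity goal; power for the NLR goal alone at 0.85/0.75 is about 0.998.

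**Conclusion.** The concern holds as a matter of wording. The 80% is equation E power for the NLR goal at sensitivity 0.90, specificity 0.50 and 20% prevalence, and it does not carry over to FNR below 5% in general. The clearest contrast is in the plan itself: 0.583 without and 0.545 with the interim at the same NLR and FNR.

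Among the points examined with NLR at or below 0.20 and specificity of at least 0.28, power falls short of 0.80 only at roughly sensitivity 0.93 to 0.955 with specificity near 0.28 to 0.35. These figures assume 20% prevalence, 400 evaluable subjects and the interval levels in 9.5.1.

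Two stronger inferences are tempting and not supported. One is that Table 10 is miscalculated; every cell reproduces. The other is that the trial is underpowered and needs more subjects. At HALT-C performance power is at least 0.996, and at sensitivity 0.95 with NLR 0.15 Table 12 gives 0.910 and 0.890. Design, sample size and the efficacy criteria are not called into question by this point.

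**What to change.** In 9.2.1, replace the FNR sentence with:

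> At sensitivity 0.90, specificity 0.50 and 20% prevalence (NLR 0.20, FNR 4.8%), power for the NLR goal at N=400 is about 0.80 by equation E; power at a given FNR depends on sensitivity, and at the same NLR and FNR with sensitivity 0.95 Table 12 gives 0.583 without and 0.545 with the interim.

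Add the same design-point condition to the 80% power statement in section 1.1. Do not quote 0.855 for sensitivity 0.90 with the interim until the futility wording in 9.5.1, which joins the two conditions, is reconciled with the rule that reproduces Table 12, under which either condition suffices.

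The cost is two short text edits using figures already in Tables 10 and 12, with no new simulation and no added subjects. The stated power will read less favourably at high sensitivity with low specificity.

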9.2.2 SECONDARY EFFICACY ENDPOINTS: SAMPLE SIZE AND POWER

The sample size of 400 evaluable subjects is determined by the statistical power requirements for the primary efficacy endpoint. The secondary efficacy endpoints will use the same subjects as the primary analysis. With 20% prevalence, the study should have a sufficient number of subjects with large esophageal varices. The number of varices and total sample size will provide adequate power for evaluation of the secondary and exploratory endpoints.

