¹ NOTE: There is some disagreement in the literature regarding the calculation of the False Negative Rate (FNR) for a test. FNR has been defined by the U.S. Food and Drug Administration in a disease-centric manner as 1 - Sensitivity ((Σ False negative) / (Σ Condition positive)), while being defined in much of the clinical literature in a test-centric manner as 1- NPV ((Σ False negative) / (Σ Predicted condition negative)). To compare to published results from the literature, in this protocol, the test-centric definition for FNR (1-NPV) has been used, and the term "miss rate" has been used to express 1-Sensitivity.

population is 20%. Each subject will have been selected to undergo a future EGD for variceal screening or surveillance according to standard criteria used in current clinical practice.

Enrolled subjects will undergo standard clinical assessment, laboratory tests, and the HepQuant SHUNT Test. The previously scheduled EGD will be performed no more than 6 weeks following the HepQuant SHUNT Test.

The relationship of DSI to large varices will be analyzed by AUROC and the diagnostic performance of the DSI cutoff \leq 18.3 will be defined by sensitivity, specificity, PPV, NPV, NLR, PLR, FNR and miss rate². The validated DSI cutoff will aid the clinician in the decision to proceed with or avoid the EGD.

Objectives:

The **primary objective** of this study is to validate DSI ≤18.3 for identifying subjects with CLD selected for future EGD for variceal screening or surveillance who are not likely to have large esophageal varices if the EGD were to be performed ("Rule Out").

The Secondary objective is to define the relationship of DSI to probability for large varices over the full range of DSI.

Exploratory objective 1 is to examine the diagnostic performance of DSI for large varices over the full range of DSI. We will generate and evaluate the AUROC (c-statistic) for DSI in likelihood of large esophageal varices. The AUROC for DSI in likelihood of large varices will be compared to the c-statistic 0.76 reported by Abrades, et al, for LSM plus platelet count (8).

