DSI ≤18.3 lowers the Miss Rate for Large Varices. Miss rate for large varices is defined by the number of cases with large varices below cutoff divided by the total number of cases with large varices. For the HALT-C Training dataset the Miss Rate was 1/22 = 4.5%. For the pooled results from the 10 published studies of LSM plus platelet count the Miss Rate was 21/319 = 6.6%. For individual published studies of LSM plus platelet count, the Miss Rate ranged from 0.0 to 18.2%.

In addition, the AUROC for DSI in likelihood of large varices was c-statistic = 0.82 which compares favorably to cstatistic = 0.76 for LSM plus platelet count, i.e., an improvement in overall diagnostic performance.

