9.5.1 PLANNED INTERIM ANALYSIS

One interim analysis is planned after the analysis data sets contain complete results (DSI measurements and EGD examination results) on at least 250 participants. The objective of the interim analysis will be to evaluate whether the interim results would allow the trial to be stopped for either efficacy or futility; i.e., because the performance goals for DSI < 18.3 as a test for ruling out large varices has been satisfied (efficacy) or because it is futile to continue because sensitivity is too low and NLR is too large.

Process for preparing and reviewing interim analysis: The trial database is maintained by an independent CRO. Trial investigators do not have access to DSI results, and the Sponsor does not have access to EGD findings. The interim analysis will therefore be performed by a statistician independent from both the sponsor and the CRO. The results of the interim analysis will be reviewed and interpreted by the independent biostatistician using the interim decision criteria to make a recommendation to HepQuant to either continue or stop the trial based on the interim results. If the determination is made to continue the trial, no further analyses will be conducted until the full recruitment is reached, and no blinded information will be provided to the sponsor, the CRO, or any investigator. If the determination is made to stop the trial, analysis of all endpoints will be performed on the interim data (N=250) according to the trial SAP.

Decision criteria for the interim analysis: The interim decision criteria are based on standard methods for group sequential clinical trial design as published by Emerson, et. al. [117] as implemented in the software package RCTdesign. With complete results on 250 subjects the independent unblinded statistician will convey one of three conclusions based on the results of the data analysis:

- i. The efficacy decision criteria have been satisfied: This conclusion is reached if:
 - a. The upper limit of the 97.64% score-based confidence interval for NLR is less than 0.52, and
 - b. the observed sensitivity greater than or equal to 0.85.
- ii. *The futility decision criteria have been satisfied:* This conclusion is reached if:
 - a. The upper limit of the 51.41% score-based confidence interval for NLR is larger than 0.52, and
 - b. the observed sensitivity less than 0.85.
- iii. Neither the efficacy nor the futility decision criteria have been satisfied.

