9.6.2 EXPLORATORY ANALYSES

Exploratory 1 (AUROC of DSI for large esophageal varices): The c-statistic for the AUROC for DSI in likelihood of large esophageal varices will be compared to the c-statistic for the AUROC of LSM plus platelet count in likelihood of large esophageal varices. The most complete study with publication of AUROCs for LSM plus platelet count is from Abraldes, et al (8) where the AUROC was 0.76 for varices needing treatment (large varices or small varices with red signs). Given this benchmark the performance goal is an AUROC \geq 0.76 for DSI in likelihood of large esophageal varices.

In addition, we will examine the diagnostic performance (sensitivity, specificity, PPV, NPV, NLR, PLR, FNR, miss rate⁸) of DSI over the full range of DSI to define the Optimal DSI for "Rule Out" – highest sensitivity and NPV with lowest FNR. We will also compare the diagnostic performance of this "optimum" DSI to DSI 18.3. The purpose of this analysis is to provide upside and downside performance of DSI around the validated cutoff of DSI 18.3.

This analysis will yield a table of sensitivities, specificities, NPVs, PPVs, NLRs, PLRs, FNRs, and miss rates⁸ over the given range of DSI that could be included in a package insert to help the clinician interpret a given DSI result.

AUROCs of DSI in likelihood of large varices will be constructed for individual etiologies of disease with over 100 subjects and for the categories of cholestatic and non-cholestatic liver diseases.

Exploratory 2 (DSI for Small or Any Size of Esophageal Varices). The analyses listed above for primary objective, secondary objective 1, and secondary objective 2 will be repeated using small varices in one set of analyses and any size of varices in another set of analyses.

Exploratory 3 (STAT). The serum concentration of d4-cholate from the 60-minute time point (STAT) of the HepQuant SHUNT test correlates well with DSI (r^2 =0.88). The STAT value represents a simplified, single point version of DSI. For this reason, we propose to evaluate the diagnostic performance of a cutoff for STAT defined from the HALT-C Training dataset for large esophageal varices and esophageal varices of any size.

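### Section 9.2.2 asserts adequate power for the exploratory endpoints, but showing that DSI's AUROC exceeds 0.76 has only about 51% power at N=400 and 35% at N=250 if the true AUROC is 0.82

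*Combined protocol and SAP*

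**What the plan says.** Section 9.2.2 explains where the sample size comes from: "The sample size of 400 evaluable subjects is determined by the statistical power requirements for the primary efficacy endpoint". It then adds that "The number of varices and total sample size will provide adequate power for evaluation of the secondary and exploratory endpoints". It gives no alternative, precision or power figure for any secondary or exploratory endpoint.

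Exploratory objective 1 includes an external comparison. Section 1.1 says: "The AUROC for DSI in likelihood of large varices will be compared to the c-statistic 0.76". Section 9.6.2 takes the benchmark from a published study of LSM plus platelet count, "where the AUROC was 0.76 for varices needing treatment", and continues: "Given this benchmark the performance goal is an AUROC" of at least 0.76. No test, alpha or confidence limit is attached to that goal.

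Other relevant text:
- Section 9.4.1 sets two-sided p<0.05 as the general significance rule and plans 95% confidence intervals for measures of diagnostic accuracy.
- Section 9.5.1 says that if the trial stops at the interim, "analysis of all endpoints will be performed on the interim data (N=250").
- Section 9.5 sets the HALT-C AUROC of 0.82 beside 0.76 and calls it "i.e., an improvement in overall diagnostic performance".

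**The concern.** The primary endpoint has a worked power evaluation (Tables 10, 12 and 13). The exploratory endpoints have one sentence. The AUROC comparison is the exploratory analysis that most resembles a claim against current practice, and the gap to be detected is small: 0.82 against 0.76.

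The smaller sample is also a likely one if the test works. Table 13 (sensitivity 0.90, 20% prevalence) gives a 65% chance of an interim efficacy stop at a true NLR of 0.20 and 88% at 0.15. Section 9.2.2 mentions only 400.

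Two misreadings are possible. An observed AUROC a little above 0.76 could be reported as an improvement over LSM plus platelets. A lower limit that fails to clear 0.76 could be taken as evidence against DSI when the sample was too small to decide.

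**Working it through.** **Inputs**
- Full sample: "A sample size of 400 participants (80 with large varices, 320 without) was selected" (section 9.2.1), so 80 cases and 320 non-cases.
- Interim sample: 250 at the same 20% prevalence, so 50 cases and 200 non-cases.
- Benchmark 0.76 (sections 1.1 and 9.6.2), treated as fixed.
- True AUROC 0.82. This is an assumption: it is the HALT-C value (sections 2.2.4, 4.2.2.1 and 9.5), since the plan states no design alternative for the AUROC.
- Two-sided 0.05 (section 9.4.1).

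**Step 1. Reproduce the plan's own figure.** Table 9 equation E with sensitivity 0.90 and specificity 0.50 gives

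V = 0.90/(0.10 × 80) + 0.50/(0.50 × 320) = 0.1125 + 0.003125 = 0.1156, with square root 0.340.

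Power = Φ(ln(0.52/0.20)/0.340 − 1.96) = 0.80, as in Table 10. The critical value is 0.52 × exp(−1.96 × 0.340) = 0.27, as stated. The primary calculation is sound.

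**Step 2. Precision of the AUROC (Hanley-McNeil).** With A the AUROC, m cases and n non-cases:

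Var = [A(1−A) + (m−1)(A/(2−A) − A²) + (n−1)(2A²/(1+A) − A²)]/(mn)

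At A = 0.82 the terms are A(1−A) = 0.1476, A/(2−A) − A² = 0.0225 and 2A²/(1+A) − A² = 0.0665.
- 80/320: (0.1476 + 79 × 0.0225 + 319 × 0.0665)/25,600 = 0.000904, SE 0.030.
- 50/200: (0.1476 + 49 × 0.0225 + 199 × 0.0665)/10,000 = 0.00145, SE 0.038.

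**Step 3. Power for the lower 95% limit to exceed 0.76.** Power = Φ(0.06/SE − 1.96).
- N=400: Φ(0.06/0.0301 − 1.96) = 51%.
- N=250: Φ(0.06/0.0381 − 1.96) = 35%.

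**Step 4. Dependence on method and assumptions.**

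| Case | N=400 | N=250 |
|---|---|---|
| Range over two-sided variants at 0.82 (null or alternative SE, Obuchowski, binormal, DeLong simulation) | 42-64% | 28-47% |
| Plain DeLong, simulated, at 0.82 | 64% | 47% |
| Logit-scale DeLong, simulated, at 0.82 | 57% | 37% |
| Highest at one-sided 0.05, at 0.82 | 75% | 58% |
| Hanley-McNeil, true AUROC 0.80 | 25% | 17% |
| Hanley-McNeil, true AUROC 0.84 | 79% | 59% |
| Hanley-McNeil at 0.82, adding the benchmark's own sampling error (57 cases, 322 non-cases, Table 2) | 23% | 20% |
| Hanley-McNeil at 0.82, benchmark 0.73 | 85% | 66% |

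Against 0.76, no variant at a true 0.82 reaches 80%.

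**Step 5. The goal as written (point estimate at least 0.76).** The chance of meeting it is Φ((A − 0.76)/SE).
- True 0.82: Φ(0.06/0.0301) = 98% at N=400; Φ(0.06/0.0381) = 94% at N=250.
- True 0.73 (SE 0.0343 and 0.0434 from the same formula): Φ(−0.03/0.0343) = 19%; Φ(−0.03/0.0434) = 24%.

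**Step 6. The HALT-C comparison in section 9.5.** With 22 cases and 195 non-cases the same formula gives SE 0.056. The 95% CI is 0.82 ± 1.96 × 0.056, about 0.71 to 0.93, which includes 0.76.

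**Step 7. The secondary endpoint under the same sentence.** Table 3 gives a DSI slope of 0.1947 with SE 0.0403. Scaling the SE by the square root of (1/m + 1/n)/(1/22 + 1/195) gives 0.022 at 80/320 and 0.028 at 50/200, hence z of about 8.7 and 6.9. Power exceeds 99% at both sizes for the full-range slope of section 9.1.2.

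**The case against.** The strongest reply is that the plan contains no formal AUROC test. Its goal is a point estimate of at least 0.76, which it meets 98% or 94% of the time at a true 0.82. A reader might infer from the 51% and 35% that the plan misses its own criterion. The documents do not support that: those figures apply only if the comparison is read as showing that DSI exceeds 0.76, which rests on the planned comparison together with the general p<0.05 rule. This part of the reply stands, and the conclusion is conditional for that reason.

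A reader might also infer a 50% false-positive rate, because a test with a true AUROC of exactly 0.76 meets the goal half the time. That does not follow. Such a test satisfies an at-least-0.76 goal, and any point-estimate threshold behaves this way at its own value. The relevant figures are those for a truly worse test, 19% and 24% at 0.73.

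Nor does the plan omit intervals. Sections 9.4.1 and 9.5.1 already provide 95% CIs for accuracy measures. What is missing is any link between the interval and the goal.

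Finally, the 9.2.2 sentence also covers the secondary endpoint, for which it is right on the full-range definition. The reply does not rescue the sentence for the AUROC comparison, where adequacy is asserted with no supporting figure.

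**Conclusion.** The point holds in a limited form. The adequate-power statement is not supported for Exploratory 1 when the comparison with 0.76 is used to claim that DSI does better. Power is about 51% (42-64%) at N=400 and 35% (28-47%) at N=250, given a true AUROC of 0.82, 20% prevalence, two-sided 0.05 and an error-free benchmark. Meeting the written goal does not by itself show improvement over LSM plus platelets.

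The size depends on the benchmark. The protocol uses 0.76 in sections 1.1, 9.5 and 9.6.2, but section 2.2.4 reports 0.73 for TE plus platelet count from the same published study. Against 0.73 the power would be about 85% and 66%.

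This is a minor point about one exploratory endpoint, and the primary endpoint is untouched. The small-varices, any-varices and STAT analyses were not checked. Nor was the secondary analysis restricted to DSI above 18.3 that section 3 describes.

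**What to change.** - **Section 9.2.2:** limit the adequate-power statement to the primary and secondary endpoints. For the AUROC comparison, state the expected precision (SE about 0.030 at N=400 and 0.038 at N=250, at AUROC 0.82) or the power range with its assumptions.
- **Section 9.6.2:** apply the 95% CI already planned in 9.4.1. Conclude improvement over the benchmark only if the lower limit exceeds it; otherwise report the point-estimate goal as descriptive. Name the interval method, and quote any power for that same method. Hanley-McNeil power should not stand beside a DeLong rule, since the two differ (51% against 64% at N=400).
- **Benchmark:** reconcile 0.76 with the 0.73 in section 2.2.4 and say which applies and why.
- **Section 9.5:** note that HALT-C's 0.82 rests on 22 cases, with a 95% CI of about 0.71 to 0.93 that includes 0.76.

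The cost is wording only, with no new data or subjects. The exploratory claim of improvement becomes harder to make.
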